The 36 different recipes were gained from the website www.eggrecipes.co.uk, developed by the British Egg Industry Council (British-Egg-Industry-Council, 2016), selected as suitable for breakfast / brunch as well for other meals, and amended to contain 25-30g of protein. Participants in the intervention group received six sets of six recipes. Each set of recipes included a variety of egg preparations (e.g. fried eggs, scrambled eggs, omelettes); a variety of preparation times and methods (hob, oven, microwave); meat, fish and vegetarian dishes; and a variety of traditional (bacon, cheese, ham) and foreign flavours e.g. Indian, Turkish, Moroccan, Italian. Several of the recipes were developed by chefs known from UK television. Recipes were printed in large clear text on glossy A5 recipe cards, to aid durability and simulate supermarket recipe cards, and included preparation time and nutritional composition, with the protein content highlighted in bold. All recipes mentioned the dish was high in protein, and recommended consumption for breakfast or brunch. Recipe cards were pilot tested with individuals in the target age group, prior to use, and the text on several recipes was altered for face validity as a result. A list of all recipes can be found in Supplementary Materials I.

All herb/spices mentioned in the recipes were also provided for one preparation of the dish as part of the intervention. Herbs/spices were provided to reduce disuse of the recipes through ingredient expense. Other ingredients were not provided to result in an intervention that could be manageable in a real life scenario.

Control

Participants in the control group did not receive any recipes, herbs or spices, or the recipe feedback forms, but received all other documentation and undertook all tests sessions in the same manner as the intervention group.

Outcomes

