Our primary outcomes were egg intake, protein intake (total), protein intake from animal-based foods and adverse events. Secondary outcomes were lean body mass and various functional measures of lean body mass. Variables of potential influence on these outcomes were also assessed, to include various demographic and lifestyle characteristics, energy intake, BMI, usual physical activity levels, health-related quality of life, reasons for eating / not eating eggs, and recipe feedback (intervention group only) Morton et al., 2017). Some of these additional variables were included in analyses to control for potential confounding, some were used only to describe the sample and some were used to investigate further any reasons for intervention success or failure.

Primary Outcomes:

Egg intake: Egg intake was measured using two measures: an egg consumption Food Frequency Questionnaire (FFQ) measure [ref] and the egg section of a validated FFQ [SCG-FFQ, Clark, 2017; Masson et al., 2003]. The egg consumption FFQ requested frequency of consumption of 18 preparations of egg: boiled eggs (hot), hard boiled eggs (cold), fried eggs, scrambled eggs, poached eggs, omelettes, scotch eggs, quiches/savoury flans, egg sandwiches, egg salad, custards, meringues, sweet flan/crème caramel, duck/quail's eggs, raw eggs, egg yolk separate from the white, and egg white separate from the yolk. For each type of egg, participants were asked to complete number of measures (e.g. 1 egg, 1 slice) consumed per day (1, 2, 3, 4, 5+) on number of days per week, using response options 1 - 7 days per week, once or twice per month, or rarely / never. Responses were converted to number of eggs eaten per month, where the category 'rarely or never' was counted as 0 times eaten per month, 'once or twice per month' as 1.5 times, and 1 to 7 days per week, as 4, 8, 12, 16, 20, 24, and 28 times per month, respectively. All foods were considered to contribute equal portions of eggs, excepting the egg dishes custards, meringues, and sweet flan / crème caramel, where each consumption was considered as 0.5 portions, because a standard portion tends to be less than one egg.

The SCG-FFQ is a validated FFQ, developed by the Scottish collaborative group, measuring dietary intake over the last two-three months (Clark, 2017; Masson et al., 2003). The section on egg intake consists of

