Usual Physical Activity: Physical activity, as energy expended in physical activity per week, was assessed using the Community Healthy Activities Model Program for Seniors (CHAMPS), a physical activity questionnaire for older adults (Stewart et al., 2001). The CHAMPS lists a variety of light, moderate and vigorous physical activities, and requests weekly frequency of performing each activity in number of hours per week (response options: less than 1 hour, 1-2.5 hours, 3-4.5 hours, 5-6.5 hours, 7-8.5 hours, and 9 or more hours). Responses were converted to four outcomes (Stewart et al., 2001), and estimated caloric expenditure per week on all activities was used for analyses. Physical activity is strongly related to muscle mass and strength (Cruz-Jentoft et al., 2010; Goodpaster et al., 2008), and a recent review showed that experience in exercise made protein supplementation with resistance training more effective (Morton et al., 2017). Studies also show associations between higher egg intake and low physical activity (Hu et al., 1999).

Health related quality of life: Health related quality of life (HR QoL) was assessed using the short form-36 questionnaire (SF-36) (Ware Jr & Sherbourne, 1992). Scores for all nine domains were generated (Ware Jr & Sherbourne, 1992) and added up to give a total SF-36 score, where a higher score suggests a greater HR QoL. SF-36 scores have been associated with muscle strength and physical performance (Syddall, Martin, Harwood, Cooper, & Sayer, 2009).

Reasons for eating or not eating eggs: Reasons for eating / not eating eggs were assessed by questionnaire, as previously developed [ref], to give insights into other possible barriers to trying the recipes.

Recipe feedback: Intervention group participants also received a recipe feedback form in the post after the 12 week intervention and after the following 12 weeks. This form asked for comments on which recipes and herb/spice packets they used or did not use, and why. Recipe feedback forms were sent by post after the test sessions, so that the completion of these does not impact on our primary outcomes, by a researcher unassociated with testing to maintain blinding.

Procedure

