A schematic overview of the study design can be found in Figure 1. All participants came to Bournemouth University for a test session at baseline (T1), after 12 weeks intervention (T2), and after a further 12 weeks (T3). A week before each test session, participants received a set of questionnaires by post, to complete and bring to the test session. Queries were discussed at the test session, but on a few occasions, participants finished the questionnaires at home within a few days after the test session, and returned them by post. All test sessions were conducted in the morning between 8.00 and 11.00, at a time of the participant's preference. Participants came fasted, and were asked to have had only water to drink since going to sleep the night before the test session. Height and weight were measured first, followed by bioelectrical impedance measures of body composition. After these measures, a breakfast of toast / cereal and coffee / tea was provided. While the participant was eating breakfast, questionnaires were checked for missing values and any queries were discussed. After breakfast, the functional measures of lean muscle mass were undertaken. Questionnaires and tests undertaken were the same for each test session (T1, T2, T3), excepting that demographic and lifestyle characteristics, and reasons for eating / not eating eggs were only assessed at baseline. Test sessions were individual, or if preferred per couple, and lasted approximately an hour per person. After the baseline test session, all participants also received a postcard with a short dietary information message, including the importance of dietary protein for older adults and why it may be beneficial to eat more protein, and to do so for breakfast. This was included to add relevance to the recipes for those in the intervention group, but made no reference to the recipes or intervention, but was identical for all participants.

Blinding:

Outcome assessments were undertaken by a researcher who was blind to intervention group ([name]). Recipes and herb/spice packets were sent to intervention participants by a researcher with no direct contact with participants ([name]). Participants were not blind, although they were blind to the other possible conditions, thus the control group did not know about the intervention, nor the details of the intervention. Participants in the intervention group were asked not to mention the recipes to researchers.

Ethical Approval and Trial Registration

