Ethical approval for this study was granted by the Research Ethics Committee of Bournemouth University, prior to commencement. Participant recruitment started in May 2016, and test sessions were run from June 2016 to April 2017. The study was registered at ClinicalTrials.gov in May 2016 (NCT02777918).

Data analyses

Data were analysed using IBM SPSS Statistics for Windows, version 22, using an Intention-to-treat approach. First, all measures were tested for normality. All baseline measures were then compared

between the intervention and control group using χ^2 tests and Mann-Whitney U tests. Demographic and lifestyle characteristics were used to describe the sample. Correlations were investigated between all baseline measures. Multiple linear regression analyses were then used for the main analyses (Vickers & Altman, 2001). The effect of the intervention on all outcome measures was assessed using multiple linear regression, controlling for age, gender, baseline measures of the dependent variable, previous participation in related studies, and measures of total protein intake, BMI, usual physical activity and HR QoL score as assessed at the same time. Previous participation was included in regression models to allow for possible demand characteristics. Energy intake was not included in regression models following high correlations with BMI. Other demographic and lifestyle characteristics were also not included to maintain statistical power (Howell, 2012]. Separate regression models were used to predict egg intake, total protein intake, protein intake from animal sources, adverse events, lean body mass, physical performance, handgrip strength, and leg extensions as the dependent variables. Similar analyses were conducted once at the end of the 12 week intervention (T2) and once at the end of the following 12 weeks (T3). Egg intakes from the two different measures were compared using correlations and multiple linear regressions were conducted for both measures. Reasons for eating / not eating eggs and details on recipe feedback will be analysed further at a later date. These data and some of the data of participant demographic and lifestyle characteristics will be published elsewhere in exploratory analyses investigating intervention success / failure. Missing data were completed using last observation carried forward. Data are reported using means and standard deviations.

Figure 1: Schematic overview of the study design

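### The first recipe feedback form goes only to the intervention group between T2 and T3, so posting it after the session does not protect the T3 egg and protein comparisons

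*Combined protocol and SAP*

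**What the plan says.** Under Additional Outcomes (Recipe feedback), the mailing schedule is: "Intervention group participants also received a recipe feedback form in the post after the 12 week intervention and after the following 12 weeks". On content: "This form asked for comments on which recipes and herb/spice packets they used or did not use, and why". On timing, the plan gives a reason: "Recipe feedback forms were sent by post after the test sessions, so that the completion of these does not impact on our primary outcomes". The same paragraph adds that a researcher not involved in testing posts the forms, to maintain blinding.

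The Control section confirms that the other arm has no counterpart: "Participants in the control group did not receive any recipes, herbs or spices, or the recipe feedback forms".

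Under Outcomes: "Our primary outcomes were egg intake, protein intake (total), protein intake from animal-based foods and adverse events". Procedure places T2 at the end of the 12-week intervention and T3 a further 12 weeks later. The outcome questionnaires and tests are the same at all three sessions. Data analyses states that similar regressions were run once for T2 and once for T3.

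**The concern.** By giving a reason for the timing, the plan accepts that completing the form could influence the primary outcomes. The reason is stated without limit, as if it covered every assessment of those outcomes. Yet a form posted after T2 is also posted before T3.

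The contact follows allocation and reaches one arm only, so randomisation does not balance it. Assessor blinding does not help either, because egg and protein intake are reported by participants who know what they received. The plan takes this kind of influence seriously elsewhere. Participants were not told the study aim, and previous participation enters the regression models to allow for demand characteristics.

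What is at stake is the meaning of T3. Recipe deliveries stop at 12 weeks, so a reader will naturally take a T3 difference as change that lasted after delivery ended. Part of it could instead reflect renewed use of the recipes, or altered reporting, after a form asking which ones were used.

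**Working it through.** **1. Order of events** (Procedure; Recipe feedback; Control)

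| Event | Intervention | Control |
|---|---|---|
| T2 session, week 12 | yes | yes |
| Form 1, posted after T2 | yes | no |
| T3 session, week 24 | yes | yes |
| Form 2, posted after T3 | yes | no |

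**2. What the timing protects**

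- Form 1 against T2: protected, with one gap. Procedure says that a few participants finished questionnaires at home within a few days of the session. The posting date of form 1 is not given, so overlap cannot be excluded for them.
- Form 2 against T3: protected, with the same small gap.
- Form 1 against T3: not protected. The documents give no control-group counterpart, no adjustment and no caveat.

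**3. How much of the T3 dietary report follows form 1**

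Primary Outcomes says that the SCG-FFQ covers the last two to three months. At 52.18 weeks per year:

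- two months = 2 × 52.18 / 12 = 8.7 weeks
- three months = 3 × 52.18 / 12 = 13.05 weeks

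T3 is 12 weeks after T2. If the questionnaire is completed at the session:

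- the two-month window opens 12 − 8.7 = 3.3 weeks after T2
- the three-month window opens 13.05 − 12 = about 1 week before T2, so 12 / 13.05 = 92% of it lies after T2

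Questionnaires are posted a week before the session. If completed on arrival, 11 weeks after T2, the three-month window still has 11 / 13.05 = 84% after T2.

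So if form 1 was posted promptly after T2 (an assumption), most or all of the diet reported at T3 follows it. No recall period is stated for the separate egg consumption FFQ.

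**4. Scale**

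The documents contain no estimate of a prompting effect. What can be shown is how sensitive a T3 protein comparison would be to one.

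The plan's own figure first. The target difference is (75 + 90)/2 − 69.8 = 12.7 g/day, with SD 20.3, two-sided alpha 5% and power 0.8:

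n = 2 × (1.96 + 0.842)² × 20.3² / 12.7² = 40.1, rounded up to 41 per group, as stated.

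With 41 per group, the unadjusted standard error of the difference is 20.3 × √(2/41) = 4.5 g/day. With no true lasting effect, an assumed form-induced shift b gives this probability of a significant difference: 1 − Φ(1.96 − b/SE) + Φ(−1.96 − b/SE).

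| Assumed b (g/day) | 0 | 1 | 2 | 3 | 5 |
|---|---|---|---|---|---|
| Chance of p < 0.05 | 5.0% | 5.6% | 7.3% | 10.3% | 20.0% |

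These values of b are hypothetical. The result is the same for a negative b, except that the excess then falls in the other direction. The planned regressions adjust for baseline and other covariates, so their standard error will differ.

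**The case against.** The strongest reply is that the form adds little to what was already there. By T2, intervention participants had received 36 recipe cards in six mailings, with the protein content in bold, and had been asked not to mention the recipes to researchers. The cards were made to be durable, and nothing says that they were collected. That stands. A reader might infer that the form first revealed the purpose of the study, or that T3 would otherwise have measured unprompted persistence. The documents support neither: awareness of the recipes existed at T2 too, and the plan never describes T3 as unprompted.

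Four other stronger readings also fail.

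- A reader might infer that the safeguard protects T2 only. It also protects T3 from the second form.
- A reader might infer that every intervention participant's T3 value is affected. Missing data are filled by last observation carried forward, so some T3 values may predate the form. The plan does not say whether drop-outs were sent one, or how many were completed.
- A reader might extend the point to adverse events. These are asked about for the previous month only, and the documents suggest no route from the form to symptoms.
- A reader might assume that the bias must favour the intervention. Asking why recipes were not used need not raise intake.

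None of this closes the gap. Prior awareness may make the effect smaller, but the stated reason for the timing still does not cover the first form at T3.

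**Conclusion.** The concern holds in a limited form. The sequence is certain from the documents: an intervention-only contact about recipe use falls between T2 and T3, and the stated safeguard does not cover it. The T3 egg and protein contrasts therefore estimate the recipes plus that contact.

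Inflation of the apparent lasting effect is possible, but neither its size nor its direction can be determined. The table above shows sensitivity only and is no estimate of bias. The statement that most or all of the T3 SCG-FFQ window follows the form rests on prompt posting after T2. The T2 comparison is largely unaffected, provided the form went out after any late T2 questionnaires had been returned. This is a matter of how T3 is described and interpreted, and does not invalidate the trial.

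**What to change.** **For a repeat study.** Send no recipe feedback form between T2 and T3. Post one form after the T3 questionnaires have been returned, asking about weeks 1-12 and weeks 13-24 separately. This saves one mailing. The cost is longer recall, over up to 24 weeks and 36 recipes, in data meant to help explain success or failure. Data analyses assigns those data to later exploratory work, so the main comparisons lose nothing.

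**For this trial.** Data collection ended in April 2017 (Ethical Approval and Trial Registration), so only reporting can change:

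- Restate the Recipe feedback sentence: posting after the session separates each form from its own session, but does not protect T3 from the first form.
- Give the posting date of the first form relative to return of the T2 questionnaires, including those finished at home.
- Report T3 egg and protein results as follow-up that includes an intervention-only feedback contact after T2.

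The cost is a few sentences and a check of the mailing records.

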three questions: number of measures (eggs) per day, and the number of days per week they eat 'Boiled or poached eggs'; 'Fried eggs'; and 'Scrambled eggs or omelette'. Response options were used and converted to monthly egg intake as above.

Protein intake: Protein intake was measured using the complete SCG-FFQ, where food intake data were converted to protein intake and protein intake from animal sources, by the Scottish collaborative group (Clark, 2017). Protein intake from animal sources consisted of protein intake from meat, fish, eggs, and dairy foods. Protein intake is known to be related to egg intake (Ruxton, Derbyshire, & Gibson, 2010, questionnaire study), to muscle mass, strength and function (Houston et al., 2008; Loenneke, Loprinzi, Murphy, & Phillips, 2016; Tieland et al., 2012), and to positive health outcomes in older adults (Hannan et al., 2000; Lord, Chaput, Aubertin-Leheudre, Labonté, & Dionne, 2007). Animal based proteins contain all essential amino acids and are considered high quality protein sources (van Vliet, Burd, & van Loon, 2015). Animal protein stimulates a higher net protein synthesis than a high plant protein diet (Pannemans, Wagenmakers, Westerterp, Schaafsma, & Halliday, 1998). These measures also allowed investigation of any replacement of other high protein foods by egg based protein foods.

Adverse events: To assess adverse events, participants were asked whether during the previous month they had experienced any of the following effects more or less often than usual: nausea, digestive issues (e.g. constipation or diarrhoea), stomach aches/cramps, hunger, bloating/uncomfortable fullness, thirst, headaches, fatigue/tiredness, restlessness, dizziness, or skin rashes. If they answered yes to any of these questions, they were asked if they knew of any reason for this, or they had experienced anything else that was different than usual.

Secondary Outcomes:

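### Questionnaires, including egg intake, are checked and queried directly before the functional tests, apparently by the blinded assessor; this order weakens the blinding of three secondary outcomes

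*Combined protocol and SAP*

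**What the plan says.** The order of a test session is set out under Procedure. "Height and weight were measured first, followed by bioelectrical impedance measures of body composition". Breakfast comes next, and during it "questionnaires were checked for missing values and any queries were discussed". Then: "After breakfast, the functional measures of lean muscle mass were undertaken".

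The same section says that the questionnaires and tests did not change between T1, T2 and T3, except that demographics and lifestyle, and reasons for eating or not eating eggs, were collected at baseline only. Both egg-intake measures and the full food frequency questionnaire are therefore among the forms at T2 and T3. A few participants finished their forms at home after the session.

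Under Blinding: "Outcome assessments were undertaken by a researcher who was blind to intervention group". The safeguard for contact at the session is that "Participants in the intervention group were asked not to mention the recipes to researchers".

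Under Adverse events, participants who report a changed symptom get an open follow-up: "they were asked if they knew of any reason for this". Whether this is on paper or in person, and when in the visit it happens, is not stated.

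**The concern.** Chair stands, balance and walking are timed, leg extensions are counted in a fixed period, and handgrip is a maximal effort. How an assessor instructs, times or counts can shift such results, and that is the reason for blinding the assessor.

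The stated order brings possible information about the group into the session just before these tests. Asking participants not to mention the recipes does not cover what they have written about egg intake. Nor does it reliably cover a query, for instance on how to record a new egg dish. If reasons for symptoms are also collected at that point, a participant could give a change in diet as the reason.

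At stake are physical performance, handgrip and leg extensions. These are three of the eight dependent variables listed under Data analyses, each modelled at T2 and again at T3.

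**Working it through.** **1. Who checks the forms.** The text is in the passive voice, so the roles have to be set side by side.
- Randomisation: done by a researcher who does not meet participants.
- Mailing of recipes and packets (Blinding): also by a researcher who does not meet participants.
- Recipe feedback forms: posted by someone not involved in testing.
- Outcome assessment (Blinding): by the blinded researcher, the only role described as involving contact at sessions.

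The assessor is therefore the likely checker. This is an inference, not a statement in the plan.

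**2. What comes before and after the check.**

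| Step in the session | Outcome | Exposed at the same session? |
|---|---|---|
| Height, weight, bioelectrical impedance | Lean body mass | No, measured before the check |
| Breakfast, forms checked, queries discussed | – | Possible disclosure |
| SPPB, leg extensions, handgrip | Three secondary outcomes | Yes |

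Ankle weight and test duration for the leg test are chosen at the first session and then kept, so later knowledge of the group cannot change them.

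**3. How the plan treats the same risk elsewhere.** Recipe feedback forms go out after the sessions, through a person outside testing, expressly to protect blinding. The egg questionnaires have no such separation, and no check that the assessor stayed blind is described.

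**4. Size, as an illustration only.** The plan's own sample size, for protein intake, is reproduced first, to fix n. With a difference of 12.7 g, SD 20.3 g, two-sided 5% and 80% power:

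n = 2 × (1.960 + 0.842)² × (20.3 / 12.7)² = 40.1, rounded up to 41 per group, as stated.

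The documents give neither an SD nor an unblinding rate for the functional tests. Assume no true effect and an arm-level shift of b SD caused by the assessor. The two-sided 5% rejection probability (normal approximation) is

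Φ(b√(n/2) − 1.96) + Φ(−b√(n/2) − 1.96).

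For n = 41, √(n/2) = 4.528; for n = 50 (the recruitment target), √(n/2) = 5.

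| Assumed b | n = 41 per arm | n = 50 per arm |
|---|---|---|
| 0 | 5.0% | 5.0% |
| 0.1 | 7.4% | 7.9% |
| 0.2 | 14.8% | 17.0% |
| 0.3 | 27.4% | 32.3% |

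A two-sided t-test with 41 per arm gives 7.3%, 14.6% and 26.9%, the same after rounding.

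**5. Dilution.** Here b is an average over the arm. If only a fraction p of one arm is unmasked, each unmasked participant must be shifted by b / p. With p = 25%, b = 0.2 needs 0.2 / 0.25 = 0.8 SD per unmasked participant. The upper rows therefore require either frequent unmasking or large individual effects.

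**The case against.** The strongest case on the other side has four parts.

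- **The checker is unnamed.** The recipe instruction speaks of researchers in the plural, so someone else may have checked the forms. This stands, and the point has to be put as apparent, not established.
- **The check is limited.** It looks for missing values and deals with queries. A reader might infer that the assessor went through every egg and adverse-event answer with the participant. The documents do not support that, and they do not place the adverse-event questions on the posted forms.
- **The signal is weak.** Controls eat eggs too, and everyone received the same postcard encouraging protein at breakfast. High egg intake hints at the group without identifying it. Explicit disclosure would come mainly from a query or a stated reason.
- **The scope is narrow.** Handgrip is a dynamometer reading (the maximum of six), walking uses the faster of two times, and SPPB components are scored 0 to 4. All are secondary outcomes.

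These arguments limit the point but do not remove it. The order is explicit, the egg forms are present at T2 and T3, and nothing in the text separates the person who handles them from the person who tests.

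**Conclusion.** The point holds as an avoidable weakness in assessor blinding for SPPB, leg extensions and handgrip at T2 and T3. It rests on one inference, that the assessor checks the forms.

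A reader might go further and conclude that the order undoes the blinding or that the functional results are biased. The documents support neither. They show an open route, not that it was used, and they give no unblinding rate. The false-positive figures of about 7%, 15% and 27% show how sensitive a comparison with 41 per arm would be to assumed shifts of 0.1, 0.2 and 0.3 SD. They do not estimate what happened here. They also come from a simple two-group comparison, whereas the planned analysis is a covariate-adjusted regression.

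Lean body mass is not exposed at the session in question. It could be affected only at T3, if the assessor remembers what was learned at T2.

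**What to change.** **For a repeat of this design:** serve breakfast with the forms closed, run all functional tests, and only then check the forms and discuss queries, taking egg and adverse-event items last. Record every case where the group became known, and whether this was before the functional tests. State in the protocol who does the check.

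**Cost:** no extra staff. The visit becomes a few minutes longer, because checking no longer overlaps with breakfast. Reordering does not stop knowledge gained at T2 from carrying over to T3. A checker other than the assessor would close that gap too, at the cost of a second person.

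**For this trial:** sessions ended in April 2017, so the order cannot be changed. The sponsor should state who checked the forms, report any known unblinding, and interpret the functional outcomes with that limitation.
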